7.3.1 Expedited Reporting Responsibilities of the Study Center

For any serious or unexpected adverse event, Perrigo must be notified **within 24 hours** of when the Investigator first learns of the occurrence of the event. Expedited reporting requirements

for serious adverse events are described below. Adequate information must be collected with supporting documentation to complete a standard report for submission to Perrigo. The adverse event term on the AE eCRF and the SAE report should agree exactly. Special attention should be given to recording hospitalizations and concomitant medications.

Subjects with unresolved adverse event(s) or serious adverse event(s) should be followed by the investigator until the events are resolved, events determined to be chronic or the subject is lost to follow-up. Resolution means the subject has returned to the baseline state of health, or the investigator does not expect any further improvement or worsening of the adverse event. The investigator should continue to report any significant follow-up information to Perrigo up to the point that the event has resolved. Any serious adverse event reported by the subject to the investigator that occurs within 30 days after the last assessment, and are determined by the investigator to be reasonably associated with the use of the study medication, should be reported to Perrigo within 24 hours of when the Investigator first learns of the occurrence of the event.

When reporting a serious adverse event (SAE) the Investigator (or the designated staff) will promptly report any serious adverse event or pregnancy by telephone to [REDACTED] immediately after the investigator becomes aware of the event. An SAE form should be completed and sent by fax, email, or overnight courier to [REDACTED] within 24 hours of knowledge of the event by the site. In many cases, only preliminary information will be available. Appropriate follow up information should be sought (hospital discharge summaries, operative reports etc.) and a follow up SAE report form submitted. A designation of causality from the study medication should always be included with a follow up report. Assess and report the causality of the event.

7.3.2 Submitting an Expedited Safety Report to the IRB

Once [REDACTED] receives all supporting documentation for the reported event, the Medical Monitor, in conjunction with Perrigo, will determine if the safety report is eligible for expedited review. [REDACTED] will log the initial event and will notify Perrigo that an event has been reported within 1 business day after initial receipt. [REDACTED] will complete the review of the event, enter information into their safety database and generate the report. This form, as well as other supporting documentation, will be forwarded to [REDACTED] Medical Monitor for review. [REDACTED] will finalize the report and distribute it to Perrigo within 2 days after initial receipt. When expedited safety reporting to regulatory authorities is indeed required, the Investigator should review and update any newly available materials at once. Follow-up queries may be issued to the study center to further clarify the event.

Each expedited safety report will routinely include a brief cover memorandum, the completed report, and any additional pertinent information recommended by [REDACTED], Perrigo, or study Medical Monitor. Once the report is assembled, the Principal Investigator must submit the

expedited safety report to the IRB within the required reporting timeframe. Follow-up reports should be submitted when requested or when pertinent information becomes available.

When a Principal Investigator receives an expedited safety report from [REDACTED] or Perrigo detailing adverse events occurring at other study centers under this protocol, it must be promptly submitted to the study center's IRB. The Principal Investigator must retain a copy of such reports as submitted to their IRB in the site's study Regulatory Binder.

7.4 SAE & AEs Requiring Discontinuation of Study Drug, including Pregnancies

ANY SAE, WHICH OCCURS AFTER A SUBJECT HAS ENTERED THE STUDY, WHETHER OR NOT RELATED TO STUDY MEDICATION, MUST BE REPORTED TO [REDACTED] AND PERRIGO IMMEDIATELY (WITHIN 24 HOURS) VIA TELEPHONE OR FACSIMILE. IF INITIALLY REPORTED VIA TELEPHONE, THIS MUST BE FOLLOWED-UP BY A FACSIMILE OF THE WRITTEN SAE REPORT WITHIN 24 HOURS OF THE CALL TO [REDACTED].

Non-serious events that require discontinuation of study medication (including laboratory abnormalities) should be reported to Perrigo immediately and within 1 working day. Subjects who discontinue due to experiencing adverse events should be followed clinically until their health has returned to baseline status, or until all parameters have returned to normal. It is expected that the investigator will provide or arrange appropriate supportive care for the subject.

A subject who experiences a severe adverse event related to study drug will be discontinued from the study.

The notification about any serious adverse event should be directed to:

[REDACTED]

[REDACTED]

[REDACTED]

7.4.1 Pregnancy

At the time a Principal Investigator or Study Coordinator becomes aware that a study participant became pregnant following study participation, the Principal Investigator or Study Coordinator will report the pregnancy immediately by phone and/or by faxing a completed Pregnancy Report to [REDACTED] within one working day of being notified of the pregnancy report.

The report will include the following elements:

- Participant (mother's) coded study identifier;
- Date of participant's last menstrual period;
- Total accumulated dose of study treatment administered to date;
- Date of study medication administration

The investigator will follow the subject until completion of the pregnancy and must assess the outcome in the shortest possible time [REDACTED] within completion of the pregnancy.

Upon delivery, miscarriage or abortion, the Principal Investigator or Study Coordinator must forward a follow-up Pregnancy Report with any relevant information on the present condition of the fetus to [REDACTED], including:

- Mother's coded study identifier(s);
- Gestational age at delivery, miscarriage or abortion;
- Birth weight, gender, length and head circumference, if available;
- Apgar scores recorded after birth, if available;
- Any abnormalities.

If the outcome of the pregnancy **meets the criteria for immediate classification of an SAE** (e.g., spontaneous or therapeutic abortion [any congenital anomaly detected in an aborted fetus is to be documented], stillbirth, neonatal death, or congenital anomaly), the investigator will report the event by phone and by faxing a completed SAE report form to [REDACTED] within one working day of being notified of the pregnancy report.

If the trial is completed before the outcome of the pregnancy is known, [REDACTED] will assume the responsibility for following up on the pregnancy. [REDACTED] will contact the Investigator or Study coordinator on or around the potential expected date of delivery to follow-up on the outcome of pregnancy and will also check on the status of the infant 8 weeks post-delivery. Upon awareness of the pregnancy outcome and known status of the infant following 8 weeks of delivery, the investigator will complete the applicable pregnancy report forms and fax to [REDACTED] within 1 day of being notified.

7.5 Post Study Adverse Events

7.5.1 Non-serious Adverse Events

Adverse events that are identified at the last assessment visit (or the early termination visit) must be recorded on the AE eCRF with the status of the AE noted.

7.5.2 Serious Adverse Events

Serious adverse events that are identified on the last assessment visit (or the early termination visit) must be recorded on the AE eCRF page and reported to Perrigo according to the procedures outlined above. Subjects with unresolved previously reported serious adverse events, or any new serious adverse events identified on the last assessment visit, should be followed by the investigator until the events are resolved, or the subject is lost to follow-up. Resolution means the subject has returned to the baseline state of health, or the investigator does not expect any further improvement or worsening of the adverse event. The investigator should continue to report any significant follow-up information to Perrigo up to the point that the event has resolved. Any serious adverse event reported by the subject to the investigator that occurs after the last assessment, and are determined by the investigator to be reasonably associated with the use of the study drug, should be reported to Perrigo.

8. STATISTICAL ANALYSIS

The sections that follow highlight sample size determination and the planned analyses for this study. A statistical analysis plan (SAP) will be prepared separately from this protocol which gives descriptions of the statistical methods, models, hypotheses and subject populations to be analyzed. The SAP will be completed and approved before locking the database and unblinding the study and will serve as a companion to the protocol and the *de facto* documentation of the proposed statistical evaluation. The SAP will be completed and finalized prior to breaking the blind.

8.1 Statistical Analysis Plan

8.1.1 Analysis Populations

The following populations are defined for the purpose of analyses:

- Intent-to-Treat (ITT) (safety population): Any subject that was randomized, and received and used study medication.

- Modified Intent-to-Treat (mITT): Any subject that was randomized, met eligibility criteria, received and used study medication, and that has at least one post-baseline efficacy assessment.

- Per Protocol (PP): Any subject:
 - Who met eligibility criteria
 - Who was randomized and received and used study medication

- Who applied the study medication on Days 1-3 [REDACTED]
- Who completed Visit 4/Day 57 (End of Study/Early Termination Visit) within window OR was discontinued from the study due to treatment failure [REDACTED]
- Without significant protocol violations that could have interfered with the administration of the treatment or the precise evaluation of treatment efficacy

[REDACTED]

[REDACTED]

8.1.2 Planned Analysis

All subjects who received study medication will be evaluated for safety. The efficacy analysis will be conducted on both the PP and the MITT subject populations. Two-sided hypothesis testing will be conducted for tests. Resulting p-values less than 0.05 will be considered statistically significant. No adjustments of p-values for multiple comparisons will be made. No interim analyses are planned. SAS software will be used for all data analyses and tabulations.

The treatment response will be summarized by treatment group for the end-of-study evaluation. The primary efficacy endpoints will be the proportion of subjects with clinical response of success defined as complete clearance (absence) of all clinically visible Actinic Keratosis lesions identified at the Baseline visit and no new Actinic Keratosis lesions in the treatment area at Visit 4/Day 57.

[REDACTED]

8.1.3 Sample Size Considerations

[REDACTED]

[REDACTED]

[REDACTED]

[REDACTED]

8.1.4 Efficacy Measures and Analysis

Clinical endpoints

The primary efficacy measure will be the proportion of subjects with clinical response of success defined as complete clearance (absence) of all clinically visible Actinic Keratosis lesions identified at the baseline visit and no new Actinic Keratosis lesions in the treatment area at Visit 4/Day 57.

Equivalent efficacy

For the proportion of subjects with clinical success, the Test treatment will be considered to be therapeutically equivalent to the Reference treatment if the 90% confidence interval on the difference between Test and the Reference proportions is contained within the interval -20% to +20%. The confidence interval will be constructed using Wald's method with Yates' continuity correction.

[REDACTED]

Superiority

Superiority will be demonstrated if both the active treatments (Test and Reference) are shown to be superior to the vehicle.

The proportion of subjects with clinical success for each active treatment will be compared to that of the Vehicle using a Z-test with Yates' continuity correction.

All hypothesis tests will be two-sided at a significance level of $\alpha = 0.05$, except confidence intervals which will be based on $\alpha = 0.10$ (i.e. 90% coverage).

[REDACTED]

[REDACTED]

8.1.5 Safety and Adverse Events Analysis

The frequency and percent of subjects with adverse events will be summarized by MedDRA system organ class and preferred term and by severity and relationship to study drug for all three treatment groups. [REDACTED]

[REDACTED]. The comparable safety of the Test and Reference treatments will be evaluated by statistical comparison of the proportion of subjects who reported any adverse events. The test and reference treatments' frequency and distribution of application site reactions of erythema, flaking/scaling, crusting, swelling, vesiculation/postulation, and erosion/ulceration will be summarized and compared descriptively. Safety comparisons will be performed only for the safety intent-to-treat population.

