Safety:	The incidence of all adverse events reported during the study will be summarized by treatment group. Equivalence of the test and reference with regard to safety will be evaluated by comparing the nature, severity and frequency of their adverse event profiles. In addition, the test and reference treatments' frequency and distribution of application site reactions of erythema, flaking/scaling, crusting, swelling, vesiculation/pustulation, and erosion/ulceration will be summarized and compared descriptively.

ABBREVIATIONS

AE	Adverse Event
AK	Actinic Keratosis
ANOVA	Analysis of Variance
ATC	Anatomic Therapeutic Chemical (classification of drugs)
eCRF	Electronic Case Report Form
EDC	Electronic Data Capture
FDA	US Food and Drug Administration
GCP	Good Clinical Practice
ICH	International Conference on Harmonization
IGA	Investigator's Global Assessment
IRB	Institutional Review Board
ITT	Intent to treat population
IUD	Intra-Uterine Device
LOCF	Last Observation Carried Forward
MedDRA	Medical Dictionary for Regulatory Activities
mITT	Modified Intent To Treat population
OTC	Over the counter
PI	Principal Investigator
PP	Per protocol population
Rx	Prescription
SAE	Serious Adverse Event
SAP	Statistical Analysis Plan
SPF	Sun Protection Factor
Sub-I	Sub-Investigator

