2.2 Safety

Safety of the test and reference products will be compared by evaluating the nature, severity and frequency of their adverse event profiles. All adverse events that occur during the study (from the moment a subject signs an informed consent) will be recorded. Descriptions of reactions or complaints will include the approximate date of onset, the date the adverse event ended, the severity of the adverse event, and the outcome. Comparisons between the

treatment groups will be made by tabulating the frequency of subjects with one or more adverse events (classified into MedDRA terms) during the study. Pearson's Chi-Square test or Fisher's Exact test, whichever is most appropriate, will be used to compare the proportion of subjects in the two active treatment groups with any adverse event. [REDACTED]

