5.10 Application Site Reaction Assessment

To the greatest extent possible, the same investigator who made Day 1 (Baseline) assessments will assess the application site reactions, grade them according to a 5-point scale and a designated staff will record them in the source document and eCRFs at each subsequent visit. This assessment must be conducted by qualified individuals listed on the Form FDA 1572 who have been delegated this task by the PI. [REDACTED]

[REDACTED]

At baseline (prior to initial dosing) and each subsequent visit, application site reactions of erythema, flaking/scaling, crusting, swelling, vesiculation/pustulation, and erosion/ulceration are to be recorded in the source document and eCRFs.

Application site reactions (erythema, flaking/scaling, crusting, swelling, vesiculation/pustulation, and erosion/ulceration) are not to be recorded as adverse events unless they result in either:

- The temporary discontinuation of the study medication.
- The discontinuation of the subject from the study.

[REDACTED]

Protocol No: PRG-NY-14-019

- The use of a new concomitant medication in order to treat this event.

Any other application site reaction not listed above (such as pain, pruritus and infection) should be recorded as adverse events in the source document and eCRFs.

The following scale will be used for the Application Site Reaction Assessment:

Site Reaction	DESCRIPTION
Erythema	[REDACTED]
Flaking/scaling	[REDACTED]
Crusting	[REDACTED]
Swelling	[REDACTED]
Erosion/ulceration	[REDACTED]
Vesiculation/pustulation	[REDACTED]

Site Reaction	Grading Criteria				
	0 (clear)	1 (almost clear)	2 (mild)	3 (moderate)	4 (severe)
Erythema	Not present	[REDACTED]	[REDACTED]	[REDACTED]	[REDACTED]
Flaking/scaling	Not present	[REDACTED]	[REDACTED]	[REDACTED]	[REDACTED]
Crusting	Not present	[REDACTED]	[REDACTED]	[REDACTED]	[REDACTED]
Swelling	Not present	[REDACTED]	[REDACTED]	[REDACTED]	[REDACTED]
Erosion/ Ulceration	Not present	[REDACTED]	[REDACTED]	[REDACTED]	[REDACTED]
Vesiculation/ pustulation	Not present	[REDACTED]	[REDACTED]	[REDACTED]	[REDACTED]

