5.1 Methodological Considerations

The study will be conducted under the same protocol across all the sites. No formal statistical analyses are planned to evaluate the consistency of efficacy results across the multiple clinical sites. These results, however, will be tabulated and if a site's efficacy data are obviously inconsistent with the results across all sites, this will be explored and addressed in the final study report.

Two-sided hypothesis testing will be conducted for all the tests. Resulting p-values less than 0.05 will be considered statistically significant unless noted otherwise. No adjustments of p-values for multiple comparisons will be made. No interim analyses are planned. SAS software will be used for all data analyses and tabulations.

5.2 [REDACTED]

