5.6 Safety Variables and Analyses

Duration of Treatment and Medication Compliance

Number of applications, days of exposure, and compliance rate will be summarized by treatment group using descriptive statistics. For each subject, the overall duration of treatment (days) will be calculated using the following formula:

$$(\text{Date of last application of study medication}) - (\text{Date of first application of study medication}) + 1.$$

Medication compliance rate (%) will be calculated for each subject as follows:

$$(\text{Total number of applications used}) / (\text{Expected number of applications}) * 100\%.$$

Subjects who complete the study are expected to have 3 applications. Subjects will only be considered compliant if they apply all three daily doses on study Days 1-3. For prematurely discontinued subjects, expected number of applications will be determined based on the overall duration of treatment by the time of discontinuation. Descriptive summaries of exposure and medication compliance rate will be provided by treatment group for the ITT subjects

Adverse Events

Adverse events (AEs) will be coded in MedDRA, version 15.1. Treatment-Emergent Adverse Event (TEAE) is defined as any AE occurs on or after applying the first dose of study drug. Number and percent of subjects reporting TEAEs will be tabulated by treatment group. Summaries will be presented by body system and preferred term for the ITT population, and further by severity and relationship to study medication. [REDACTED]

[REDACTED] In the summaries of incidence rates (frequencies and percentages), severity and relationship to study drug, subjects who report more than one event that are mapped to the same preferred term will be counted only once under the strongest severity and relationship, accordingly Fisher's exact test will be used to compare the proportions of subjects of the two active treatment groups who report any TEAE.

Treatment-Emergent Serious Adverse Events (TESAEs) will be discussed within the clinical study report. TESAEs and TEAEs that led to treatment interruption or discontinuation will be presented in data listings.

Concomitant Medications

Concomitant medications will be coded using the WHO Drug Dictionary, version September 2014, and will be presented in data listings.

Application Site Reactions

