The severity of application site reactions such as erythema, flaking/scaling, crusting, swelling, vesiculation/pustulation, and erosion/ulceration will be summarized by treatment group and visit using frequencies and percentages of subjects.

[REDACTED]

6 Appendices

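### Comparable safety of Test and Reference rests, in the visible text, on a difference test of any adverse event; a non-significant result does not show comparability, and the six graded site reactions are compared only descriptively

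*Protocol*

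**What the plan says.** The first-named objective covers both the safety and the efficacy profiles of the two active gels (Protocol 2, SAP 2). For safety, the Synopsis states: "Equivalence of the test and reference with regard to safety will be evaluated by comparing the nature, severity and frequency" of the adverse event profiles. Protocol 8.1.5 says that comparable safety "will be evaluated by statistical comparison of the proportion of subjects who reported any adverse events".

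The test is named in two places. Protocol 2.2 leaves a choice: "Pearson's Chi-Square test or Fisher's Exact test, whichever is most appropriate, will be used to compare the proportion of subjects" with any adverse event in the two active arms. SAP 5.6 settles it: "Fisher's exact test will be used to compare the proportions of subjects of the two active treatment groups who report any TEAE". SAP 5.1 adds "Two-sided hypothesis testing will be conducted for all the tests" and "Resulting p-values less than 0.05 will be considered statistically significant unless noted otherwise".

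Protocol 5.10 determines what counts as an adverse event. Erythema, flaking/scaling, crusting, swelling, vesiculation/pustulation and erosion/ulceration "are not to be recorded as adverse events unless they result in either" an interruption of study medication, withdrawal from the study, or a new medication to treat the reaction. Other local reactions, such as pain, pruritus and infection, are recorded as adverse events. The six listed reactions are graded 0 to 4 at baseline and at each later visit. Protocol 8.1.5 compares them descriptively, and under SAP 5.6 their severity "will be summarized by treatment group and visit using frequencies and percentages of subjects".

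**The concern.** The stated aim is to show that two products are alike in safety, but the only inferential comparison in the visible text is built to detect a difference. Its null hypothesis is equality, so failing to reject it may mean that the rates are close or that the trial was too small to tell. The smaller the trial, the more often the second explanation applies. The plan handles this correctly for efficacy: Protocol 8.1.4 and SAP 5.5 use a 90% confidence interval with limits of ±20 points. The visible safety text has no corresponding interval or margin.

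The choice of variable adds to this. Protocol 7 lists local skin reactions first among the common reactions to the reference product. The six graded reactions enter the tested proportion only when a trigger is met, so a difference between Test and Reference in those reactions may not reach the test. What is at stake is the weight that a report can place on a statement of comparable safety. The primary efficacy conclusion is not affected.

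**Working it through.** **Inputs from the documents.** Two-sided Fisher's exact test at 0.05 on any treatment-emergent adverse event, Test against Reference, in the safety (ITT) population (SAP 5.1 and 5.6, Protocol 8.1.5). There is no stated power or precision figure for safety to reproduce.

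**Assumptions.** Sample size and allocation are redacted, and adverse event rates are not given. I take equal active arms of n = 100, 200 and 300, with true any-event rates between 20% and 45%.

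**Step 1: chance of a non-significant result.** With X ~ Bin(n, p_T) and Y ~ Bin(n, p_R), sum P(X = x)·P(Y = y) over all tables whose Fisher p-value is not below 0.05.

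| Reference, Test | n = 100 | n = 200 | n = 300 |
|---|---|---|---|
| 20%, 20% | 96.7% | 96.3% | 96.1% |
| 20%, 30% | 68.7% | 40.3% | 21.6% |
| 30%, 40% | 73.7% | 48.2% | 29.7% |
| 30%, 45% | 46.5% | 14.6% | 3.9% |
| 20%, 40% | 15.6% | 0.9% | 0.0% |

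**Step 2: what non-significance tells the reader.** Compare the first two rows. At n = 100 a non-significant result is only 0.967/0.687 = 1.4 times as likely under equal rates as under a 10-point excess. At n = 200 the ratio is 0.963/0.403 = 2.4, and at n = 300 it is 0.961/0.216 = 4.4.

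**Step 3: what an interval would show.** For 20% against 30%, the 95% half-width is 1.96·√[(0.20·0.80 + 0.30·0.70)/n] = 1.96·√(0.37/n), which gives 11.9, 8.4 and 6.9 points at n = 100, 200 and 300. With 1.645 in place of 1.96 (90% coverage) it is 10.0, 7.1 and 5.8 points.

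**Step 4: a single observed result.** With 30/100 on Reference, 44/100 on Test is still non-significant by Fisher's test. The 90% Wald interval with continuity term 1/n is 0.14 ± [1.645·√((0.44·0.56 + 0.30·0.70)/100) + 0.01] = 0.14 ± 0.121, or +1.9 to +26.1 points. At n = 200, 79 against 60 events is likewise non-significant, with an interval of +1.2 to +17.8 points. In both cases the p-value alone reads as no difference, while the interval shows an excess that could be large.

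**Step 5: the tested variable.** Setting Protocol 5.10 beside SAP 5.6, a graded reaction that meets none of the three triggers is not an adverse event and so cannot enter the tested proportion, whatever its grade. It does appear in the site-reaction tables by group and visit. The visible text gives no Test minus Reference estimate or interval for it.

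**The case against.** The strongest reply is that the plan contains no pass rule. A reader might infer that a p-value above 0.05 will be declared comparable safety, or that a worse Test product would pass. No visible sentence says so: SAP 5.1 says only when a result is significant. Fisher's test is also not the whole safety evaluation. Adverse events are tabulated by system, term, severity and relationship, and site reactions are compared descriptively. This stands. The problem is that the one inferential tool offered cannot support the stated aim, and that the plan does not rule out the wrong reading.

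A reader might also infer that the adverse event rule loses the graded reactions or removes most local toxicity from the comparison. The documents support neither. The reactions have their own scale and tables. Pain, pruritus, infection and any graded reaction that meets a trigger remain adverse events, so the excluded share cannot be quantified.

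Nor can one conclude that worst grades or unscheduled-visit grades go unreported. Text is redacted directly after the site-reaction sentence in SAP 5.6, and the unscheduled-visit procedures in Protocol 5.12.6 are redacted. There are also redactions next to the test sentence in Protocol 2.2, before the key sentence in Protocol 8.1.5 and within the adverse event paragraph of SAP 5.6, so a further safety rule cannot be excluded.

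The size depends on the scenario. For a 20-point excess (20% against 40%), Fisher's test is significant in 84% of trials at 100 per arm and 99% at 200. This is fair; it shows that the test is weak for moderate excesses, not for every excess.

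Finally, an interval without a margin is not a decision rule. That is true, and a margin would be a further choice. With equal true rates of 20% to 40% and 80% power, n = (1.645 + 1.282)²·2p(1−p)/m² gives 69 to 103 per arm for m = 20 points and 275 to 412 for m = 10 points. An interval is still useful without a margin, because it shows which excess the data leave open.

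**Conclusion.** The point holds within limits. The plan aims at equivalence or comparable safety, and the only inferential safety comparison in the visible text is a two-sided difference test whose non-significance does not show comparability. That logic does not depend on the redacted figures. Its size does: under assumed rates of 20% and 30% with equal arms, a 10-point excess goes undetected in 69%, 40% and 22% of trials at 100, 200 and 300 per arm, while a 20-point excess goes undetected in 16% at 100 per arm and in under 1% at 200. The six graded reactions are outside the tested variable by default and are compared descriptively, by group and visit. They are absent from the test, not from the report. The conclusion is limited to visible text and goes no further than that.

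**What to change.** In Protocol 2.2 and 8.1.5 and SAP 5.6, base the comparability statement on the Test minus Reference difference in the proportion with any treatment-emergent adverse event, with its confidence interval. State the coverage level explicitly, because Protocol 8.1.4 sets 90% for confidence intervals and a reader may otherwise expect 95%. Fisher's test can stay as supportive. Add one sentence saying that p above 0.05 is not read as equivalence.

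Unless the redacted text already does so, report the same difference and interval for each subject's worst post-baseline site-reaction grade over all recorded visits, at a cut fixed before unblinding. Grade 3 or higher is one example; the choice belongs to the sponsor.

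The cost is wording in two documents and two small tables from data already collected, with no added subjects or visits. The drawback for the sponsor is a less favourable safety statement, since the interval displays what has not been excluded.
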